6.3.2. Handling of Dropouts and Missing Data

If patients withdraw consent from the study before the Week 25 visit, no further data will be collected, and only tumor scans up until the date of withdrawn consent will be included in the evaluation of tumor response. Missing MRI data will not be imputed. Patients with missing MRI data at the Week 25 visit will be considered as non-responders.

6.3.3. Primary Analysis of Primary Efficacy Endpoint

The primary BIRC-25-Week ORR based on RECIST v1.1 will be analyzed based on the ITT analysis set. The ORR will be compared at a two-sided significance level of 0.05 using Fisher's exact test. Fisher's exact test is considered the preferred method for this primary analysis, particularly due to the expectation that the number of anticipated response events might be less than 5 within stratified placebo groups based on the historical data.

The 95% confidence interval (CI) for the difference in ORR (ABSK021 - placebo) will be calculated using the Wilson method. The option RISKDIFF (CL = WILSON) will be used in SAS PROCFREQ procedure. The exemplary SAS code for the primary analysis is presented below.

```
PROC FREQ DATA= dataset;
CLASS treatment response;
TABLES treatment * response / ALPHA = 0.05 RISKDIFF (CL = WILSON);
EXACT FISHER;
RUN;
```

The number and percentage of patients in each category of Best Overall Response (BOR) by the BIRC (CR, PR, SD, non-CR/non-PD/non-NE, PD, or NE) will be presented by treatment group. A similar summary of the primary ORR for each treatment group along with their exact two-sided 95% CIs using the Clopper-Pearson method will be provided.

In addition, summaries will be performed on the BIRC-assessed tumor size of target lesions:

- The absolute values and percentage changes in target lesion tumor size from baseline by BIRC will be descriptively summarized and presented by visit and treatment group.
- The best percentage change from baseline (i.e., the maximum reduction from baseline or the minimum increase from baseline in the absence of a reduction) in the sum of diameters of target lesions will be descriptively summarized.
- The best percentage change from baseline in tumor size for each patient will also be presented graphically using waterfall plots. Reference lines at the +20% and -30% change in tumor size levels will be added to the plots, which correspond with the definitions of progression and 'partial' response respectively.

Detailed tumor assessment data from the BIRC will be listed for all randomized patients.

6.3.4. Sensitivity Analyses of the Primary Efficacy Endpoint

The following sensitivity analyses are planned to evaluate robustness of the primary analysis of the primary ORR based on the ITT analysis set.

- The treatment effect on the BIRC-25-Week ORR will be evaluated using Fisher's exact test with mid p-value correction (Lydersen et al^{3,4}, 2003, 2009). Fisher's exact test is considered the preferred method for this primary analysis, particularly due to the expectation that the number of anticipated response events might be less than 5 within stratified placebo groups based on the historical data. The corrected p-value will be calculated by subtracting half of the probability of the observed table from Fisher's p-value as shown below:

Fisher's corrected p-value = 2-sided Fisher's p-value – (Table probability)/2

- The treatment effect on the BIRC-25-Week ORR will be evaluated using a stratified Cochran–Mantel–Haenszel (CMH) method to account for the stratified factor of region (China vs. non-China sites). The adjusted proportion difference (ABSK021- Placebo) and its 95% CI will be calculated using CMH-weighted method (Kim⁵, 2013).

6.3.5. Supplemental Analyses of the Primary Endpoint

The ORR may be summarized by treatment group based on Per Protocol Set (PPS). This analysis will employ the same methodology used in the primary efficacy analysis, incorporating both Fisher's exact test with or without mid p-value correction and the stratified Cochran–Mantel–Haenszel (CMH) method. Furthermore, for the PPS, the number and percentage of patients in each category of Best Overall Response (BOR) by the BIRC (CR, PR, Non-CR/Non-PD/Non-NE, SD, PD, NE) will be presented. A similar summary of the primary ORR for each treatment group along with their exact two-sided 95% CIs using the Clopper-Pearson method will be provided.

6.3.6. Subgroup Analyses

Subgroup analyses for the primary BIRC-25-Week ORR will also be performed within the following subgroups to assess whether study drug exhibits a consistent treatment effect across each of these subgroups.

- Age Group (< 40years, ≥ 40years, ≥ 40 - < 65 years, ≥ 65 years)
- Sex (Female vs. Male)
- Region Category 1 (China vs. ex-China)
- Region Category 2 (China vs. North American vs. EU)
- Race Category 1 (Asian vs. non-Asian)
- Race Category 2 (Caucasian, non-Caucasian)
- Ethnicity (Hispanic or Latino vs. Not Hispanic or Latino)
- Lower extremity tumors vs. upper extremity tumors
- Knee vs. Others
- TCGT type (localized-type vs. Diffuse-type)
- ECOG PS (0 vs.1)

Statistical Analysis Plan for Protocol ABSK-021-301

- Number of prior surgeries (0 vs. ≥ 1)
- Prior systemic therapy (Yes vs. No)

For each subgroup defined above, the same approach employed in the primary analysis of the primary ORR will be used. These subgroup analyses are considered exploratory in nature and will not involve adjustments for multiple comparisons. A forest plot illustrating the difference in ORR (ABSK021- Placebo) and its corresponding 95% CI (Wilson method) will be produced for each subgroup. If any subgroup contains an insufficient number (i.e. less than 5) of patients for meaningful analysis, the data for those subgroups will be presented descriptively rather than being subjected to statistical testing.

6.4. Key Secondary Efficacy Endpoints Analysis – Part 1

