6.4.6. Subgroup Analysis of Key Secondary Endpoints

Subgroup analysis of key secondary endpoints will follow the subgroups classification for primary efficacy endpoint in [Section 6.3.6](#).

The evaluation for binary endpoint will use the same approach as the primary efficacy endpoint ORR.

The evaluation for continuous endpoints will use a similar approach for the primary analysis of each key secondary endpoint, with the addition of three fixed factors (subgroup, subgroup-by-treatment and subgroup-by-treatment-by-time) into the corresponding MMRM model.

6.5. Other Secondary Efficacy Analyses at the End of Study Part 1

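### The ORR subgroup analysis asks whether the effect is consistent but tests only for zero effect within each level, with a floor of 5 patients at which Fisher's test cannot reject

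*SAP*

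**What the plan says.** SAP 6.3.6 gives the purpose of the subgroup analyses of the primary ORR: "to assess whether study drug exhibits a consistent treatment effect across each of these subgroups". The method for each level is that "the same approach employed in the primary analysis of the primary ORR will be used", and SAP 6.3.3 defines that approach: "The ORR will be compared at a two-sided significance level of 0.05 using Fisher's exact test", with a Wilson interval for the difference.

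Three further sentences in 6.3.6 matter:

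- Display: "A forest plot illustrating the difference in ORR (ABSK021- Placebo) and its corresponding 95% CI (Wilson method) will be produced for each subgroup".
- Status: "These subgroup analyses are considered exploratory in nature and will not involve adjustments for multiple comparisons".
- Small levels: "If any subgroup contains an insufficient number (i.e. less than 5) of patients for meaningful analysis", then "the data for those subgroups will be presented descriptively rather than being subjected to statistical testing". A level with 5 or more patients in total is therefore tested.

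SAP 6.4.6 sends the binary key secondary endpoint (TVS-ORR) to the same approach. For the continuous key secondary endpoints it uses the primary model "with the addition of three fixed factors (subgroup, subgroup-by-treatment and subgroup-by-treatment-by-time) into the corresponding MMRM model".

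Two other places bear on this. SAP 4.1.2 states the same consistency aim but speaks only of descriptive summaries. Protocol 7.4.4.1.2 also prescribes the primary ORR approach within each subgroup, with descriptive reporting where numbers are insufficient, but gives no number.

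**The concern.** Consistency is a statement about levels compared with each other: its null is that the effect is equal across them. The Fisher test planned in each level has a different null, that the effect in that level is zero. Whether it rejects depends heavily on how many patients the level contains. A large level with p < 0.05 beside a small level with p > 0.05 is what one expects from a common effect, and also what real heterogeneity can produce. The p-values therefore cannot separate the two.

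For the binary endpoints no planned quantity addresses the stated question directly. For the continuous endpoints the model at least contains subgroup-by-treatment terms, although 6.4.6 does not say that an interaction estimate will be reported.

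The floor is a separate defect. It counts patients over both arms, so it does not guarantee a usable placebo arm, and it admits levels in which the test cannot reject at all.

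What is at stake is how the subgroup table is read, not the trial's primary result.

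**Working it through.** **Inputs.** From SAP 1.3: ORR 40% vs 6%, 2:1 allocation, Fisher's exact test at two-sided 0.05, 75 evaluable and about 90 enrolled. From Protocol 1.2.2: phase 1 ORRs at 50 mg of 58.3% (14/24) and 77.4% (24/31), used as alternative active-arm rates. Subgroup sizes are not in the documents; the splits of 90 patients below are assumptions.

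**1. The plan's own figure.** Exact binomial enumeration of Fisher's test at 50:25, 40% vs 6%, gives 90.3% power with 0.025 in each tail, and 92.3% with the usual two-sided p-value (the sum over tables no more likely than the observed one). The stated 90% is reproduced. The usual two-sided p-value is used from here on.

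**2. Smallest attainable p.** This occurs when every ABSK021 patient and no placebo patient responds.

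- 3:2: 1/C(5,2) = 1/10 = 0.10. At 4:1 it is 0.20.
- 4:2: 1/C(6,2) = 1/15 = 0.067.
- 5:2: 1/C(7,2) = 1/21 = 0.048. This is the first of these sizes at which rejection is possible, with power of 0.9% at 40% vs 6%.

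**3. Power within a level, identical effect everywhere, 2:1 allocation.**

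| Level size | 40% vs 6% | 58.3% vs 6% | 77.4% vs 6% |
|---|---|---|---|
| 15 | 12% | 44% | 77% |
| 18 | 11% | 48% | 87% |
| 30 | 40% | 83% | 98% |
| 45 | 70% | 96% | 99.9% |
| 60 | 84% | 99% | >99.9% |
| 72 | 91% | 99.9% | >99.9% |

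**4. Chance that exactly one of two levels is significant.** With powers a and b in the two levels, this is a(1 − b) + b(1 − a). For 60/30 at 40% vs 6%: 0.84 × 0.60 + 0.40 × 0.16 = 0.504 + 0.064 = 0.57. For 45/45: 2 × 0.70 × 0.30 = 0.42.

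| Split | 40% vs 6% | 58.3% vs 6% | 77.4% vs 6% |
|---|---|---|---|
| 45/45 | 42% | 7% | 0.1% |
| 60/30 | 57% | 17% | 2% |
| 72/18 | 82% | 52% | 13% |

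At 40% vs 0% the figures are 8%, 42% and 84%.

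**5. The forest plot read against zero.** If the Wilson intervals are read only by whether they exclude zero, discordance at 40% vs 6% is 40%, 50% and 72% for the same splits. The plot helps only if levels are compared with each other or with the overall estimate.

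**6. A direct comparison of levels.** Simulation (200,000 runs) of a z-test on the difference between the two ORR differences, with Agresti-Caffo variances and the same 40% vs 6% in both levels, flagged a difference in 2.3% to 2.6% of trials over these splits and 81/9.

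**7. Worked example (hypothetical counts).**

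- Level A, 16/40 vs 1/20: difference 0.35, Wilson interval 0.119 to 0.509, Fisher p = 0.005.
- Level B, 8/20 vs 1/10: difference 0.30, Wilson interval −0.054 to 0.529, p = 0.20.
- Between-level difference: 0.35 − 0.30 = 0.05.
- MOVER lower limit: 0.05 − √[(0.350 − 0.119)² + (0.529 − 0.300)²] = 0.05 − 0.325 = −0.27.
- MOVER upper limit: 0.05 + √[(0.509 − 0.350)² + (0.300 + 0.054)²] = 0.05 + 0.388 = 0.44.

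The two p-values suggest a contrast. The estimate says that the effects are close and the precision is poor.

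**The case against.** The strongest reply is that the plan never tells anyone to read the p-values as evidence on consistency. SAP 6.2 treats p-values outside the testing hierarchy as nominal measures of strength of association, 6.3.6 calls the subgroup work exploratory, and 4.1.2 describes it as descriptive. No rule declares a level with p > 0.05 inconsistent. The forest plot of differences with Wilson intervals is a standard consistency display. All of this stands, and it confines the point to a risk of misreading.

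A reader might infer more: that Fisher p-values are the plan's only means of judging consistency, so that a common effect will usually look inconsistent. The documents do not support that. The plot is planned, and the size of the problem depends on the true effect. SAP 1.3 builds 40% and 6% conservatively, from 85% of a lower confidence limit and from an upper confidence limit. At the phase 1 rates, discordance for even or 2:1 splits is much lower, and it stays large mainly for very unequal splits. Nor do the documents show that any named subgroup will be small.

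A reader might also infer that the Fisher tests must go. Protocol 7.4.4.1.2 prescribes them, so removing them is a departure from the protocol, and the remedy does not require it.

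Finally, the between-level interval will be imprecise: in simulation at 40% vs 6%, its median width was about 65 to 69 percentage points for the 45/45 and 60/30 splits. That is true, but it reports honestly what the data can say.

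None of this answers two points: no planned ORR quantity estimates the difference between levels, and the floor of 5 in total does not work for the test it governs.

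**Conclusion.** The point holds as a low-cost improvement, not as a flaw in the trial's main inference. For ORR and TVS-ORR, the only hypothesis test in the subgroup plan has the wrong null for the stated aim, and the between-level difference is not estimated. A level of 5 or 6 patients would be tested with no possibility of rejection.

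With identical effects, the chance of one significant and one non-significant level ranges from 42% to 82% at the planned rates, from 7% to 52% at 58.3% vs 6%, and from 0.1% to 13% at 77.4% vs 6%, over splits from 45/45 to 72/18. These figures rest on assumed split sizes, exact 2:1 allocation within levels and independent levels. The minimum-p results rest on none of these rates.

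The primary test, the gatekeeping sequence and type I error are untouched. The evidence does not support saying that a common effect will generally appear inconsistent; it supports saying that the within-level p-values cannot settle the question.

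**What to change.** In SAP 6.3.6, and for TVS-ORR in 6.4.6:

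1. Keep the ORRs, the differences and the Wilson intervals in the forest plot.
2. For each factor add the difference between levels in the ORR difference, with a 95% CI (for example MOVER from the Wilson limits, which can be computed with zero placebo responders), labelled exploratory and imprecise. For factors with more than two levels, name the reference level.
3. State that the within-level Fisher p-values are nominal and do not address consistency. If the sponsor prefers to drop them, in line with the descriptive wording of 4.1.2, record the departure from Protocol 7.4.4.1.2 in SAP section 9, which now lists no changes.
4. Replace the floor of 5 in total with a minimum per arm, below which only counts are shown. The value is a judgement. Five per arm means about 15 patients at 2:1, where power at the planned rates is still only 12%, so the minimum protects the display rather than creating a useful test.

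The cost is SAP wording and one more column in the plot, with no new data. The downside is wide between-level intervals, which should be described as such.

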6.4.1. Definitions of Key Efficacy Endpoints

6.4.1.1. BIRC-25-Week ORR Based on Tumor Volume Score (TVS)

The BIRC-25-Week ORR based on TVS measures the proportion of patients who achieve a BOR of either CR or PR as assessed by BIRC within 25 weeks. This assessment is based on the tumor scans that are scheduled on Day 1/Week 13 and Day 1/Week 25 according to TVS criteria detailed in the protocol [section 6.3.2](#). TVS-based tumor response assessments are similar to RECIST v1.1 with necessary clarifications described in [Table 6.1](#) above. All MRI scans will be only read in a blind manner according to the procedures outlined in Blinded Independent Review Charter for this study.

Similarly, BIRC-25-Week ORR based on TVS will be calculated based on all randomized patients. The calculation of the ORR will follow the same rules outlined for the primary efficacy endpoint in terms of handling intercurrent events.

6.4.1.2. Relative Range of Motion (ROM)

For the assessment of the range-of-motion endpoint, raw measurements of the affected joint across different motion types will be performed using a goniometer and expressed in degrees (Protocol Section 6.3.3) at Screening, Week 13 and Week 25 visits in Study Part 1. To obtain a normalized assessment, measurements of a joint and motion type will be standardized to the full range of motion (ROM) for that joint, resulting in a relative value. As shown in [Table 6.2](#), the standard full range of motion value for a given joint and motion type is calculated as the sum of standard reference values based on the American Medical Association disability criteria (Gerhardt JJ⁶, 2002). Consequently, the relative ROM value for a given joint and motion type will be calculated as follows.

$$\text{Relative ROM value (\%)} = 100 \times (\text{absolute ROM value}) / (\text{ROM full range value})$$

For instance, if a patient's measurements for shoulder's extension and flexion are 40 degrees and 170 degrees respectively, and the full range value for that joint is 230 degrees, the relative ROM for shoulder Extension-0-Flexion type would be 91.3% (calculated as $100 * (40 + 170) / 230$).

Table 6.2 Standard Reference Value of ROM Assessment

Statistical Analysis Plan for Protocol ABSK-021-301

Location	Motion Type	Standard Reference Value (Degree)	Full Range of Motion (Degree)
Shoulder	Extension -0- Flexion	50 -0- 180	230
	Abduction -0- Adduction	160 -0- 30	190
	External Rotation -0- Internal Rotation	90 -0- 90	180
Elbow	Extension -0- Flexion	0-0-135	135
	(Hyper) Extension -0- Flexion	10-0-135	145
Wrist	Extension -0- Flexion	60 -0- 50	110
Thumb (MCP joint)	Extension -0- Flexion	0-0-60	60
Thumb (IPP joint)	Extension -0- Flexion	30-0-80	110
Fingers (MCP joint)	Extension -0- Flexion	20-0-90	110
Fingers (PIP joint)	Extension -0- Flexion	0-0-100	100
Fingers (DIP joint)	Extension -0- Flexion	0-0-100	100
Hip	Extension -0- Flexion	30 -0- 100	130
	Abduction -0- Adduction	45 -0- 30	75
	External Rotation -0- Internal Rotation	50 -0- 40	90
Knee	Extension -0- Flexion	0 -0-150	150
	(Hyper) Extension -0- Flexion	10 -0- 150	160
Ankle	Dorsiflexion -0- Plantar flexion	20 -0- 40	60

Statistical Analysis Plan for Protocol ABSK-021-301

Location	Motion Type	Standard Reference Value (Degree)	Full Range of Motion (Degree)
Foot	Eversion -0- Inversion	20 -0- 30	50

MCP: Metacarpophalangeal joints. IPP: Interphalangeal joint. PIP: Proximal interphalangeal joints. DIP: Distal interphalangeal joints.

The last non-missing value of ROM on or before the randomization will be used as a baseline. If multiple records for the same joint location are measured by different motion types at the baseline, the motion type with the smallest (worst) relative ROM will be used as the baseline and this motion type will be used for evaluating the relative ROM subsequently. In the event of ties of more than one motion type at baseline, the average of relative ROM values for all such motion types will be calculated for each post-baseline ROM assessment. The post-baseline records will follow the same joint locations and motion types chosen at baseline.

The change from the baseline in ROM will be calculated for each scheduled visit by subtracting the baseline value from each post-baseline value. If either the baseline value or the post-baseline value is missing, the change will be set as missing.

6.4.1.3. Worst Stiffness Numeric Rating Scale (NRS)

Speck R. et al. (2019 [7](#)) described the content validity of the measures of these 2 PROs for patients with tenosynovial giant cell tumors (TGCT). Worst Stiffness NRS and PROMIS-PF have good reliability, validity, and responsiveness, and provide guidance for the interpretation of meaningful change in TGCT patients (Speck R. et al. 2020⁸). The Worst-Stiffness-NRS item is a one-item self-administered questionnaire assessing the “worst” stiffness in the last 24 hours. The NRS for this item ranges from 0 (“no stiffness”) to 10 (“stiffness as bad as you can imagine”). The instrument will be measured at Screening, Week1, Week 5, Week 9, Week 13, Week 17, Week 21 and Week 25 visits during Study Part 1. Except for Week 1 (C1D1), patients are required to complete the Worst-Stiffness-NRS assessments for at least 4 of 7 consecutive days during each scheduled visit. The assessment at Week 1 (C1D1) should be completed prior to the first dosing. Consequently, a minimum of 4 out of the consecutive 7 days will be required to compute the mean of NRS score for each post-dose visit; otherwise, it will be set to missing. The baseline will be derived based on the mean score of evaluations completed prior to randomization, specifically, at least 4 of 7 consecutive days during the 2 weeks prior to randomization, and on C1D1. If there are multiple consecutive 7-day assessments, the baseline will be calculated using the most recent 7-day assessments, in addition to C1D1.

The change from baseline will be calculated for each scheduled visit by subtracting the mean baseline value from each post-baseline mean value. If either the baseline value or the post-baseline value is missing, the change will be set as missing.

6.4.1.4. BPI Worst Pain Numeric Rating Scale (NRS)

The BPI-Worst-Pain-NRS item is a one-item self-administered questionnaire assessing the “worst” pain in the last 24 hours. The NRS for this item ranges from 0 (“no pain”) to 10 (“pain as bad as you can imagine”). The instrument will be measured at Screening, Week1, Week 5, Week 9, Week 13, Week 17, Week 21 and Week 25 visit during Study Part 1. Except for Week 1

(C1D1), patients are required to complete the Worst-Pain-NRS assessments for at least 4 of 7 consecutive days during each scheduled visit. The assessment at Week 1 (C1D1) should be completed prior to the first dosing. Consequently, a minimum of 4 out of the consecutive 7 days will be required to compute the mean of NRS score for each post-dose visit; otherwise, it will be set to missing. The baseline will be derived based on the mean score of evaluations completed prior to randomization, specifically, at least 4 of 7 consecutive days during the 2 weeks prior to randomization, and on C1D1. If there are multiple consecutive 7-day assessments, the baseline will be calculated using the most recent 7-day assessments, in addition to C1D1.

The change from baseline will be calculated for each scheduled visit by subtracting the mean baseline value from each post-baseline mean value. If either the baseline value or the post-baseline value is missing, the change will be set as missing.

6.4.1.5. PROMIS Physical Function (PROMIS-PF) Scale

Physical function items relevant to the assessment of lower and upper limb function have been selected from the PROMIS-PF Bank v2.0. The customized scale includes two different sets of topics for the upper and lower extremities (protocol Appendix 12.6). A total of 13 items assessing lower extremity function will be used for patients with lower extremity tumors, and 11 items for assessing upper extremity function will be used for patients with upper extremity tumors. The PROMIS- PF will be measured at Screening, Week 1, Week 5, Week 9, Week 13, Week 17, Week 21 and Week 25 visits during Study Part 1.

The HealthMeasures Scoring Service Platform (see [Appendix 3](#)) will be used to score customized PROMIS items by utilizing the response pattern scoring approach, which is especially useful when there is missing data. The platform that uses response pattern scoring can produce a T-score for a respondent as long as 1 item has been answered. However, to produce a precise score using response pattern scoring, a patient must answer at least 4 items in a short form that includes 4 or more items.

The raw score (i.e., 1-5) for each item from each patient at each visit will be uploaded to the above-mentioned Service Platform for scoring. The steps to utilize the Service Platform are detailed in [Appendix 3](#). The Platform will convert raw scores into a T-score for each patient at each visit. The T-score rescales the raw score into a standardized score with a mean of 50 and a standard deviation (SD) of 10. Therefore, a person with a T-score of 40 is one SD below the mean. The T-score ranges from 0 to 100, with a higher score indicating better physical function status.

The raw scores collected during the screening period (within 14 days before randomization) and on C1D1 will be converted to T-scores before calculating the baseline T-score average. The change from baseline will be calculated for each scheduled visit by subtracting the mean baseline value from each post-baseline mean value. The change will be set as missing if either the baseline or post-baseline values are missing.

